#### Assessment of Causality

- The investigator is obligated to assess the relationship between study intervention and each occurrence of each AE/SAE. The investigator will use clinical judgment to determine the relationship.
- A "reasonable possibility" of a relationship conveys that there are facts, evidence, and/or arguments to suggest a causal relationship, rather than a relationship cannot be ruled out.
- Alternative causes, such as underlying disease(s), concomitant therapy, and other risk factors, as well as the temporal relationship of the event to study intervention administration will be considered and investigated.
- The investigator will also consult the IB and/or Product Information, for marketed products, in their assessment.
- For each AE/SAE, the investigator **must** document in the medical notes that he/she has reviewed the AE/SAE and has provided an assessment of causality.
- There may be situations in which an SAE has occurred, and the investigator has minimal information to include in the initial report to sponsor or designee. However, it is very important that the investigator always make an assessment of causality for every event before the initial transmission of the SAE data to sponsor or designee.
- The investigator may change their opinion of causality in light of follow-up information and send an SAE follow-up report with the updated causality assessment.
- The causality assessment is one of the criteria used when determining regulatory reporting requirements.

#### Follow-up of AEs and SAEs

- The investigator is obligated to perform or arrange for the conduct of supplemental measurements and/or evaluations as medically indicated or as requested by sponsor or designee to elucidate the nature and/or causality of the AE or SAE as fully as possible. This may include additional laboratory tests or investigations, histopathological examinations, or consultation with other health care professionals.
- If a participant dies during participation in the study or during a recognized follow-up period, the investigator will provide sponsor or designee with a copy of any post-mortem findings including histopathology.

## 10.3.5. Reporting of SAEs

## **SAE Reporting via an Electronic Data Collection Tool**

- The primary mechanism for reporting an SAE will be the electronic data collection tool.
- If the electronic system is unavailable, then the site will use the SAE paper form (see next section) to report the event within 24 hours.
- The site will enter the SAE data into the electronic system as soon as it becomes available.
- After the study is completed at a given site, the electronic data collection tool will be taken off-line to prevent the entry of new data or changes to existing data.
- If a site receives a report of a new SAE from a study participant or receives updated data on a previously reported SAE after the electronic data collection tool has been taken off-line, then the site can report this information on an SAE paper form (see next section) or to the Lilly-designated medical monitor/SAE coordinator by telephone.
- Contacts for SAE reporting can be found in site training materials.

## SAE Reporting via Paper Form

- Facsimile transmission of the SAE paper form is the preferred method to transmit this information to the Lilly-designated medical monitor or the SAE coordinator.
- Initial notification via telephone does not replace the need for the investigator to complete and sign the SAE CRF pages within the designated reporting time frames.
- Contacts for SAE reporting can be found in site training materials.

## **10.3.6. Regulatory Reporting Requirements**

## SAE Regulatory Reporting

- Prompt notification by the investigator to the sponsor of an SAE is essential so that legal obligations and ethical responsibilities toward the safety of participants and the safety of a study intervention under clinical investigation are met.
- The sponsor has a legal responsibility to notify both the local regulatory authority and other regulatory agencies about the safety of a study intervention under clinical investigation. The sponsor will comply with country-specific regulatory requirements relating to safety reporting to the regulatory authority, IRB/IEC, and investigators.
- An investigator who receives an investigator safety report describing an SAE or other specific safety information (for example, summary or listing of SAEs) from the sponsor will review and then file it along with the IB and related BDCU study documents and will notify the IRB/IEC, if appropriate according to local requirements.

# **10.4.** Appendix 4: Contraceptive and Barrier Guidance

#### 10.4.1. Definitions

#### Woman of Childbearing Potential (WOCBP)

Females are considered a WOCBP if they have had at least 1 cycle of menses. Any amount of spotting should be considered menarche.

#### Women in the following categories are not considered WOCBP

Females are considered women not of childbearing potential if:

- they have a congenital anomaly such as Mullerian agenesis
- they are infertile due to surgical sterilization, or
- they are postmenopausal.

Examples of surgical sterilization include hysterectomy, bilateral oophorectomy, or tubal ligation.

#### **Postmenopausal State**

The postmenopausal state should be defined as:

- 1. A woman at any age at least 6 weeks postsurgical bilateral oophorectomy with or without hysterectomy, confirmed by operative note; or
- 2. A woman at least 40 years of age and up to 55 years old with an intact uterus, not on hormone therapya, who has had cessation of menses for at least 12 consecutive months without an alternative medical cause, AND with an FSH >40 mIU/mL; or
- 3. A woman 55 or older not on hormone therapy, who has had at least 12 months of spontaneous amenorrhea, or
- 4. A woman at least 55 years of age with a diagnosis of menopause prior to starting hormone replacement therapy.

a Women should not be taking medications during amenorrhea such as oral contraceptives, hormones, gonadotropin-releasing hormone, anti-estrogens, selective estrogen receptor modulators, or chemotherapy that could induce transient amenorrhea.

## **10.4.2.** Females

# WOCBP who are completely abstinent as their preferred and usual lifestyle, or in a same sex relationship, as part of their preferred and usual lifestyle

Must	Must Not
agree to either remain abstinent, or stay in a same sex relationship without sexual relationships with males	
 
use periodic abstinence methods         
 
calendar
 
ovulation
 
symptothermal, or
 
post-ovulation
 
 
 
declare abstinence just for the duration of a trial, or
 
use the withdrawal method.
 

# WOCBP who are NOT completely abstinent as their preferred and usual lifestyle, or in a same sex relationship, as part of their preferred and usual lifestyle

Торіс	Condition
Pregnancy testing	Negative serum result at screening followed by a negative serum result at randomization.
Contraception	Agree to use 1 highly effective method (less than 1% failure rate) of contraception, or a combination of 2 effective methods of contraception.
	These forms of contraception must be used for the duration of the study.

## **Examples of different forms of contraception:**

Methods	Examples
Highly effective contraception	
 
combination oral contraceptive pill and mini pill
 
implanted contraceptives
 
injectable contraceptives
 
contraceptive patch (only women <198 pounds or 90 kg)
 
total abstinence
 
vasectomy (if only sexual partner)
 
fallopian tube implants (if confirmed by hysterosalpingogram)
 
combined contraceptive vaginal ring, or
 
intrauterine devices
 

Effective contraception	
 
male or female condoms with spermicide
 
diaphragms with spermicide or cervical sponges
 
barrier method with use of a spermicide         
 
condom with spermicide
 
diaphragm with spermicide, or
 
female condom with spermicide
 
 
 
Note: The barrier method must include use of
 

	a spermicide (that is, condom with spermicide, diaphragm with spermicide, female condom with spermicide) to be considered effective.
Ineffective forms of contraception	
 
spermicide alone
 
immunocontraceptives
 
periodic abstinence
 
fertility awareness (calendar method, temperature method, combination of above 2, cervical mucus, symptothermal)
 
withdrawal
 
post coital douche
 
lactational amenorrhea
 

Please also refer to Sections 5.1 and 5.2.

# 10.4.3. Males

No male contraception required except in compliance with specific local government study requirements. See Section 5.1.

# 10.5. Appendix 5: Liver Safety: Suggested Actions and Follow-Up Assessments

#### **Close hepatic monitoring**

Laboratory tests (Section 10.2, Appendix 2), including alanine aminotransaminase, aspartate aminotransferase, alkaline phosphatase, total bilirubin level, direct bilirubin, gamma-glutamyl transferase, and creatine kinase, should be repeated within 48 to 72 hours to confirm the abnormality and to determine if it is increasing or decreasing, if one or more of these conditions occur:

If a participant with baseline results of	develops the following elevations:
ALT or AST <1.5x ULN	ALT or AST ≥3x ULN
ALP <1.5x ULN	ALP ≥2x ULN
TBL <1.5x ULN	TBL $\geq 2x$ ULN (except for participants with Gilbert's syndrome)
ALT or AST ≥1.5x ULN	ALT or AST $\geq 2x$ baseline
ALP ≥1.5x ULN	ALP ≥2x baseline
TBL≥1.5x ULN	TBL $\geq$ 1.5x baseline (except for participants with Gilbert's syndrome)

Abbreviations: ALP = alkaline phosphatase; ALT= alanine aminotransaminase; AST = aspartate aminotransferase; TBL = Total bilirubin level; ULN = Upper Limit of Normal

If the abnormality persists or worsens, clinical and laboratory monitoring, and evaluation for possible causes of abnormal liver tests should be initiated by the investigator in consultation with the Lilly-designated medical monitor (CRP/CRS). At a minimum, this evaluation should include physical examination and a thorough medical history, including symptoms, recent illnesses (for example, heart failure, systemic infection, hypotension, or seizures), recent travel, history of concomitant medications (including over-the-counter), herbal and dietary supplements, history of alcohol drinking and other substance abuse.

Initially, monitoring of symptoms and hepatic biochemical tests should be done at a frequency of 1 to 3 times weekly, based on the participant's clinical condition and hepatic biochemical tests. Subsequently, the frequency of monitoring may be lowered to once every 1 to 2 weeks, if the participant's clinical condition and lab results stabilize. Monitoring of ALT, AST, ALP, and TBL should continue until levels normalize or return to approximate baseline levels.

Comprehensive hepatic evaluation

A comprehensive evaluation should be performed to search for possible causes of liver injury if one or more of these conditions occur:

If a participant with baseline results of	develops the following elevations:
ALT or AST <1.5x ULN	ALT or AST $\geq 3x$ ULN with hepatic signs/symptoms a , or
	ALT or AST ≥5x ULN
ALP <1.5x ULN	ALP ≥3x ULN
TBL <1.5x ULN	TBL $\geq 2x$ ULN (except for participants with Gilbert's syndrome)
ALT or AST ≥1.5x ULN	ALT or AST $\geq 2x$ baseline with hepatic signs/symptoms a , or
	ALT or AST ≥3x baseline

ALP ≥1.5x ULN	ALP ≥2x baseline
TBL≥1.5x ULN	TBL $\geq$ 2x baseline (except for participants with Gilbert's syndrome)

Abbreviations: ALP = alkaline phosphatase; ALT= alanine aminotransaminase; AST = aspartate aminotransferase; TBL = Total bilirubin level; ULN = Upper Limit of Normal

a Hepatic signs/symptoms are severe fatigue, nausea, vomiting, right upper quadrant abdominal pain, fever, rash, and/or eosinophilia >5%.

At a minimum, this evaluation should include physical examination and a thorough medical history, as outlined above, as well as tests for PT-INR; tests for viral hepatitis A, B, C, or E; tests for autoimmune hepatitis; and an abdominal imaging study (for example, ultrasound or CT scan).

Based on the participant's history and initial results, further testing should be considered in consultation with the Lilly-designated medical monitor, including tests for hepatitis D virus, cytomegalovirus, Epstein-Barr virus, acetaminophen levels, acetaminophen protein adducts, urine toxicology screen, Wilson's disease, blood alcohol levels, urinary ethyl glucuronide, and blood phosphatidylethanol. Based on the circumstances and the investigator's assessment of the participant's clinical condition, the investigator should consider referring the participant for a hepatologist or gastroenterologist consultation, magnetic resonance cholangiopancreatography, endoscopic retrograde cholangiopancreatography, cardiac echocardiogram, or a liver biopsy.

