## 7.1.1. Liver Chemistry Stopping Criteria

The study drug should be interrupted or discontinued if one or more of these conditions occur:

Elevation from baseline	Exception
ALT or AST >8x ULN	
ALT or AST >5x ULN for more than 2 weeks	
ALT or AST >3x ULN and either TBL >2x ULN or	In participants with Gilbert's syndrome, doubling of
INR >1.5	direct bilirubin should be used for drug interruption/
	discontinuation decisions rather than TBL>2x ULN.
ALT or AST $>3x$ ULN with the appearance of fatigue,	
nausea, vomiting, right upper quadrant pain or	
tenderness, fever, rash, and/or eosinophilia (>5%)	
ALP $>3x$ ULN, when the source of increased ALP is	
the liver	
ALP >2.5x ULN and TBL >2x ULN	In participants with Gilbert's syndrome, doubling of
	direct bilirubin should be used for drug interruption/
	discontinuation decisions rather than TBL>2x ULN.
ALP >2.5x ULN with the appearance of fatigue,	
nausea, vomiting, right upper quadrant pain or	
tenderness, fever, rash, and/or eosinophilia (>5%)	
Source: FDA Guidance for Industry: Drug-Induced Live	r Injury: Premarketing Clinical Evaluation, July 2009,
and other consensus guidelines, with minor modification	S

Abbreviations: ALP = alkaline phosphatase; ALT= alanine aminotransaminase; AST = aspartate aminotransferase; FDA = Food and Drug Administration; INR = International normalized ratio; TBL = Total bilirubin level; ULN = Upper Limit of Normal

Resumption of the study drug can be considered only in consultation with the Lilly-designated medical monitor and only if the liver test results return to baseline and if a self-limited non-drug etiology is identified.

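### For raised baseline ALT/AST or ALP, the Appendix 5 repeat-test and evaluation triggers can lie above the Section 7.1.1 stopping levels, and a 7.1.1 stop does not itself trigger either action

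*Protocol*

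**What the plan says.** Protocol Section 7.1.1 lists conditions for interrupting or discontinuing study drug, all in ULN multiples. One is "ALT or AST >5x ULN for more than 2 weeks". Another begins "ALT or AST >3x ULN and either TBL >2x ULN or" and ends with INR >1.5. Others are ALT/AST >3x ULN with symptoms, ALP >3x ULN of hepatic source, and a symptomatic ALP row that begins "ALP >2.5x ULN with the appearance of fatigue". Study drug may be resumed "only if the liver test results return to baseline and if a self-limited non-drug etiology is identified".

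Appendix 5 (Section 10.5) governs follow-up. Under close hepatic monitoring, a panel of liver tests "should be repeated within 48 to 72 hours to confirm the abnormality and to determine if it is increasing or decreasing" once a trigger is met. The panel ends with "direct bilirubin, gamma-glutamyl transferase, and creatine kinase"; PT-INR is not in it. For baselines of 1.5x ULN or more the triggers are relative to baseline: twice baseline for ALT/AST, and "ALP ≥2x baseline" for ALP. The comprehensive evaluation, which does include PT-INR, starts for such baselines at "ALT or AST ≥3x baseline" without symptoms, at twice baseline with symptoms, and at twice baseline for ALP. Neither trigger table caps these multiples in ULN terms, and neither lists a 7.1.1 condition. The only Appendix 5 item tied to stopping drug is the fifth hepatic safety CRF condition. It covers discontinuation for a hepatic event and concerns data collection only.

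Exclusion criterion 25 (Section 5.2) admits screening ALT/AST up to 3x ULN and ALP up to 2.5x ULN, and allows NAFLD. The affected baselines are therefore eligible.

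**The concern.** Close monitoring and work-up would normally start at or before the level at which drug is stopped. Here the two scales differ. The stops are fixed in ULN, while the follow-up triggers rise with baseline. A participant who enters with raised enzymes can reach a stopping level while the plan still calls for no repeat test and no evaluation.

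Two stops also need data that the plan does not order at that level. A rise above 5x ULN lasting more than 2 weeks cannot be established from one draw, and the INR limb cannot be read without an INR. For stops readable from one draw, the drug is interrupted or stopped whatever Appendix 5 says; what is missing is the timed confirmation and the defined tests. The stake is participant safety in a small subset, not the efficacy conclusions.

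**Working it through.** The plan gives no figure of its own here, so the check is threshold arithmetic. B is the baseline in multiples of ULN.

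**Inputs.** Eligible ceilings (criterion 25, screening values): ALT/AST 3x, ALP 2.5x. Appendix 5 triggers for B of 1.5x or more: ALT/AST repeat 2B; ALT/AST evaluation 2B with symptoms, 3B without; ALP repeat and evaluation 2B. Stops: Section 7.1.1.

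**Formulas.** Crossover baseline = stop / multiple. Width of the uncovered range = trigger − stop, when positive.

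**1. ALT/AST repeat against the sustained >5x stop.** Crossover: 5 / 2 = 2.5x.

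| B | 2B | 2B − 5 |
|---|---|---|
| 2.5 | 5.0 | 0 |
| 2.75 | 5.5 | 0.5 |
| 2.9 | 5.8 | 0.8 |
| 3.0 | 6.0 | 1.0 |

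A participant going from 2.9x to 5.5x is above the 5x level but below the 5.8x trigger. Appendix 5 orders no repeat, so whether the rise lasts more than 2 weeks is not established under it.

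**2. ALP repeat and evaluation against the >3x hepatic-source stop.** Crossover: 3 / 2 = 1.5x.

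| B | 2B | 2B − 3 |
|---|---|---|
| 1.5 | 3.0 | 0 |
| 2.0 | 4.0 | 1.0 |
| 2.4 | 4.8 | 1.8 |
| 2.5 | 5.0 | 2.0 |

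ALP rising from 2.4x to 4x, of hepatic source, meets the stop but triggers neither action. Against the symptomatic stop at >2.5x, 2B is at least 3.0, so the gap exists at every B of 1.5x or more: 3.0 − 2.5 = 0.5 at B 1.5x, and 5.0 − 2.5 = 2.5 at B 2.5x.

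**3. Symptomatic ALT/AST evaluation against >3x with symptoms.** Crossover: 3 / 2 = 1.5x. Width: 4.0 − 3 = 1.0 at B 2x; 6.0 − 3 = 3.0 at B 3x.

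**4. PT-INR against >3x with INR >1.5.** PT-INR is not among the scheduled tests in Appendix 2 and is not named in the 48-72 h panel. Appendix 5 names it in the comprehensive evaluation and the associated test menu. Without symptoms, the ALT/AST trigger for that evaluation is 5x ULN for baselines below 1.5x, and 3B otherwise. The range above 3x where the ALT/AST rows do not call for it is therefore 5 − 3 = 2.0 for normal baselines, 6.0 − 3 = 3.0 at B 2x, and 9.0 − 3 = 6.0 at B 3x. This point does not depend on a raised baseline.

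**Cross-link.** Section 7.1.1 orders neither the repeat nor the evaluation, and neither Appendix 5 trigger table refers back to 7.1.1. A 7.1.1 interruption, unlike a discontinuation, does not meet the fifth CRF condition either.

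**The case against.** The strongest reply is that baseline multiples are deliberate. NAFLD is allowed, and purely ULN-based triggers would flag stable raised values. Appendix 5 is also headed as suggested actions. That supports keeping the multiples below the stopping levels; it does not explain letting them pass those levels.

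There are real backstops. Section 8.2.4 asks for clinically significant abnormal values to be repeated. Section 7.1 calls for appropriate measures and a sponsor alert when drug is withdrawn for a laboratory value. Section 8 asks for immediate safety concerns to be raised with the sponsor. Section 10.3 covers adverse-event follow-up, Appendix 2 allows extra tests, and the restart conditions require liver tests back at baseline and a cause identified. Some follow-up is therefore likely. But several of these rest on judgment, and none sets a 48-72 h repeat or a defined liver work-up.

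The 7.1.1 column is headed as elevation from baseline. Its entries are still ULN multiples, and every example above is a rise from baseline.

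Four stronger readings are tempting but not supported:

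- *The >8x stop goes unmonitored.* The evaluation trigger 3B does exceed 8x for B above 8 / 3 = 2.67x. But the repeat fires at 5.3-6x for B of 2.67-3x and leads to an evaluation with the medical monitor if the abnormality continues. Only the fixed minimum work-up lags.
- *Bilirubin has a similar repeat-test gap.* In 7.1.1, bilirubin >2x ULN counts only alongside raised ALT/AST or ALP. With enzyme baselines below 1.5x, the ALT/AST row fires at 3x or the ALP row at 2x. A repeat-test gap needs a raised enzyme baseline as well.
- *A higher Week 0 value widens the gap.* Appendix 5 does not define baseline. The SAP's last-value rule is an analysis definition, not one given to sites for this purpose.
- *Participants go 14 or 26 weeks untested.* Those are the scheduled chemistry intervals (Week 12 to 26; 26 to 52; 52 to 78). They apply only if every backstop fails.

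**Conclusion.** The point holds as a cheap safety improvement. At eligible screening limits, the uncovered range reaches 1.0x ULN for the ALT/AST repeat (B 3x), 2.0x ULN for ALP against its >3x stop (B 2.5x), and 3.0x ULN for the symptomatic ALT/AST evaluation (B 3x). The most consequential case is the sustained >5x stop, because without a further draw it cannot be applied. The separate PT-INR omission concerns a required input for another stop; INR remains available at the investigator's discretion and on the evaluation menu, but it is not set at that level.

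This assumes that the site's baseline lies within the criterion 25 limits and that Appendix 5 is followed as written. The widths are distances in ULN, not risks. The documents give no count of participants with such baselines. Section 2.2 reports no increased hepatic risk in Phase 2, and the efficacy conclusions are unaffected.

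**What to change.** Amend Appendix 5 in three places.

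1. For baselines of 1.5x ULN or more, set the repeat-test trigger to the lower of the baseline multiple and the 7.1.1 level: ALT/AST >5x ULN, ALP >3x ULN. Both caps sit above the entry limits (3x and 2.5x), so stable raised values are not flagged at entry.
2. Add interruption or discontinuation of study drug under Section 7.1.1 as a trigger for the repeat test and the hepatic safety CRF, with the extent of any further evaluation agreed with the medical monitor. That discretion matters: a participant with NAFLD going from ALT 2.9x to 3.1x with nausea (3.1 / 2.9 − 1 = 6.9%) meets a stop with little change.
3. Name PT-INR in the 48-72 h panel.

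A remainder is accepted. For raised ALT/AST baselines, the repeat panel still does not bring in INR between 3x ULN and the capped trigger. That range is min(2B, 5) − 3, or 1.0 at B 2x and 2.0 at B 2.5x or more.

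The cost is an amendment to protocol wording and a few unscheduled blood draws with PT-INR, plus whatever further evaluation the medical monitor agrees, in a small subset whose size the documents do not give. Near the ALP entry limit the cap is sensitive: at B 2.5x a rise of 3 / 2.5 − 1 = 20% reaches it.

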# Additional hepatic data collection (hepatic safety CRF) in study participants who have abnormal liver tests during the study:

Additional hepatic safety data collection in hepatic safety CRFs should be performed in study participants who meet 1 or more of the following 5 conditions:

- 1. Elevation of serum ALT to  $\geq$ 5x ULN on 2 or more consecutive blood tests (if baseline ALT <1.5x ULN).
  - In participants with baseline ALT  $\geq 1.5x$  ULN, the threshold is ALT  $\geq 3x$  baseline on 2 or more consecutive tests.
- 2. Elevated TBL to ≥2x ULN (if baseline TBL <1.5x ULN) (except for cases of known Gilbert's syndrome).
  - In participants with baseline TBL  $\geq 1.5x$  ULN, the threshold should be TBL  $\geq 2x$  baseline.
- 3. Elevation of serum ALP to ≥2x ULN on 2 or more consecutive blood tests (if baseline ALP <1.5x ULN).
  - In participants with baseline ALP  $\geq 1.5x$  ULN, the threshold is ALP  $\geq 2x$  baseline on 2 or more consecutive blood tests.
- 4. Hepatic event considered to be an SAE.
- 5. Discontinuation of study intervention due to a hepatic event.

Note: The interval between the 2 consecutive blood tests should be at least 2 days.

